5.4 PARTICIPANT WITHDRAWAL OR TERMINATION

5.4.1 REASONS FOR WITHDRAWAL OR TERMINATION

Participants are free to withdraw from participation in the study at any time upon request. An investigator may terminate participation in the study if:

- Any clinical serious adverse events related or unrelated to the study.
- The participant meets an exclusion criteria (either newly developed or not previously recognized) that precludes further participation.

5.4.2 HANDLING OF PARTICIPANT WITHDRAWALS OR TERMINATION

If the participant withdraws or terminates participation in the study prior to randomization to one of the intervention arms, no attempt for follow up will be made.

If the participant withdraws or terminates participation in the study after randomization to one of the intervention, we will attempt to contact them via phone calls for safety follow up. No other outcome measures will be collected.

If the participant in the study develops serious adverse events (SAEs), they will be terminated from further participation in the study. They will be referred for appropriate evaluation and treatment (if already not being done). They will be followed up until resolution of the adverse events.

Version 01.2 Protocol:201607761 Version 20.2 Version 01.2

5.5 PREMATURE TERMINATION OR SUSPENSION OF STUDY

Circumstances that may warrant termination or suspension include, but are not limited to:

- Determination of unexpected, significant, or unacceptable risk to participants
- Poor recruitment and/or completion rates

6 STUDY AGENT

6.1 STUDY AGENT(S) AND CONTROL DESCRIPTION

6.1.1 ACQUISITION

The study drug (fluoxetine) and placebo are compounded by Belmar Research, Lakewood Colorado but will be dispensed by Investigational Drug Service, University of Iowa Hospitals and Clinics.

6.1.2 FORMULATION, APPEARANCE, PACKAGING, AND LABELING

Blue opaque capsule, no lettering or embossing

6.1.3 PRODUCT STORAGE AND STABILITY

NA

6.1.4 PREPARATION

Belmar Research will use commercially available generic fluoxetine for the study but will prepare identical placebo.

6.1.5 DOSING AND ADMINISTRATION

Once a day by mouth

6.1.6 ROUTE OF ADMINISTRATION

Oral

6.1.7 STARTING DOSE AND DOSE ESCALATION SCHEDULE

10 mg once a day for one week, 20 mg once a day for one week, 40 mg once a day for two weeks, 20 mg once a day for one week and 10 mg once a day for one week. Then STOP.

6.1.8 DOSE ADJUSTMENTS/MODIFICATIONS/DELAYS

Subjects will be allowed to take 40 mg/day of drug vs placebo for maximum of an extra 1 week in case of delay in follow up appointment.

6.1.9 DURATION OF THERAPY

6 weeks

6.1.10 TRACKING OF DOSE

Phone follow up and counting pill in the pill container at follow up visit.

6.1.11 DEVICE SPECIFIC CONSIDERATIONS

NA

Version 01.2 Protocol:201607761 06/28/2017

6.2 STUDY AGENT ACCOUNTABILITY PROCEDURES

Belmar Research will be responsible for compounding. But, Investigational Drug Services, Department of pharmaceutical care at the University of Iowa Hospitals & Clinics will be responsible for storing, labelling and dispensing of the drugs.

7 STUDY PROCEDURES AND SCHEDULE

7.1 STUDY PROCEDURES/EVALUATIONS

7.1.1 STUDY SPECIFIC PROCEDURES

- Review medical history using electronic medical record, interviewing the potential subjects and use Iowa SSRI screening questionnaire.
- Medication history will be reviewed by direct interview with the subjects
- Screening for pregnancy will be done using questionnaire and urinary pregnancy test as applicable
- HCVR testing will be performed (as applicable) for baseline assessment prior to randomization and a follow up HCVR testing after randomized to an intervention arm.
- Eligible subjects will answer Iowa SSRI study questionnaire, and PHQ-9 scale
- Assessment of study drug adherence will be done by follow up phone calls and direct pill count at follow up visit
- Continuous comprehensive respiratory monitoring (respiratory inductance plethysmography abdominal and chest belts, nasal pressure, oro-nasal thermistry, pulse oximetry and transcutaneous carbon dioxide) will be done when the subjects are in EMU.

7.1.2 STANDARD OF CARE STUDY PROCEDURES

Continuous video EEG study in EMU

7.2 LABORATORY PROCEDURES/EVALUATIONS

7.2.1 CLINICAL LABORATORY EVALUATIONS

Urine pregnancy test (as applicable) will be done prior to HCVR.

HCVR testing in EMU:

Ultima PFX with gas chromatography machine will be used for HCVR testing. The machine will be operated by a well-trained respiratory therapist.

Subjects enrolled in EMU will have their baseline HCVR testing at the bedside either in a sitting up in their bed or in a chair. And those newly enrolled or follow up subjects in neurology clinic will have their

Version 01.2 Protocol:201607761 Version 20.2 Version 01.2

HCVR testing in CRU. Subject will wear a noise cancelling headphone and will be asked to look at a white/blank screen during the procedure.

The subjects will apply a nasal clip and then breathe through through a Y-valve that allows switching from room air to a 5-liter rebreathing bag filled with 50% oxygen, 6% carbon dioxide, and balance nitrogen. The test will begin with measurement of baseline respiratory parameters- respiratory rate, minute ventilation, tidal volume, ETCO₂, end-tidal oxygen breathing in room air for 2 minutes. They will then asked to hyperventilate to bring their ETCO₂ to 30 mm Hg.Then, they will be switched to a rebreathing bag. The subjects will be instructed to take 2 deep breaths promote rapid equilibration of PCO2 between the rebreathing bag and the alveolar, arterial and mixed venous compartments and then however they feel to make themselves comfortable.

The test will be terminated for: (1) ETCO₂ > 55 mm Hg; (2) ETO₂ < 160 mm Hg; (3) minute ventilation > 100 liters/minute; and/or (4) subject intolerance.

At the end of the test, the subjects will be asked to fill out questionnaire regarding their experience during the tests.

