4 STUDY DESIGN AND ENDPOINTS

4.1 DESCRIPTION OF THE STUDY DESIGN

Double blind placebo-controlled randomized prospective trial

Two enrolling locations: EMU and Neurology Clinic

1) To test effect of Fluoxetine on HCVR: Subjects will be screened in the EMU and neurology clinic. Subjects eligible are those with patients with epilepsy who have a reduced baseline HCVR slope (<2.0 L/min/mmHg). Subjects will be enrolled, and randomized to either fluoxetine or placebo (1:1) until 20 subjects complete the study. Investigational Drug Services (IDS), at the University of Iowa Hospitals and Clinics (UIHC), will be responsible for randomizing and dispensing the

Version 01.2 Protocol:201607761 Version 20.2 Version 01.2

drugs. Both fluoxetine and placebo will be encapsulated in identical casing to mask their identity. Both the subjects and the investigators will be blinded to the randomization process. A standard titration plan will consist of fluoxetine or placebo 10 mg per day for a week, then 20 mg per day for a week and then 40 mg per day for 2 weeks, upon discharge. Subjects will return after 4 weeks for follow up HCVR testing in the Clinical Research Unit at UIHC. For each subject, the magnitude of post-treatment HCVR in terms of HCVR slope, minute ventilation, VRTCO₂, time to VRTCO₂ and time to target ETCO₂ at the end of the study will be compared with their baseline HCVR. The medication adherence rate, safey concerns and change in mood scale will be assessed at follow up. Reported adverse effects will be collected for all subjects. Enrolment rate and study completion rates will also be assessed every 6 months.

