5.2 PARTICIPANT EXCLUSION CRITERIA

- 1. Progressive neurological disease.
- 2. Clinical diagnosis of bipolar disease, panic disorder, psychosis or severe depression, or PHQ-9 score > 20
- 3. Patients with prior hospitalization related to depression or Electroconvulsive therapy.
- 4. History of suicidal ideation or intent in past or present
- 5. Clinical history or laboratory evidence of hepatic or renal insufficiency.
- 6. Pregnant or lactating women.
- 7. Current heavy alcohol use (>14 drinks per week for men or >7 drinks per week for women) or) known medical disorder related to alcohol use or current illicit drug use.
- 8. Patients with recent use (<1 month) or already taking fluoxetine or other selective serotonin reuptake inhibitors (SSRIs).
- 9. Concurrent use of monoamine oxidase inhibitors, antipsychotic agents, antidepressant agents other than SSRIs or frequent use of triptan agents (>2/week).
- 10. History of a previous allergic reaction or adverse effects with fluoxetine, hypersensitive reaction-anaphylaxis; laryngeal edema; hives
- 11. History of serotonin syndrome.
- 12. History of uncontrolled pulmonary or cardiac illness.
- 13. Patients with normal hypercapnic ventilatory response, i.e. HCVR slope of ≥ 2.0
- 14. Patients with known prolong QT interval
- 15. Patients with family history of prolong QT interval
- 16. Patients with family history of sudden cardiac death.

Version 01.2 Protocol:201607761 06/28/2017

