7.3 STUDY SCHEDULE

7.3.1 SCREENING

Potential subjects for the study will be are referred by treating neurologists at neurology clinic & EMU at the University of Iowa Hospitals & Clinics.

- Referred subjects are screened based on review of medical history & Iowa SSRI screening questionnaire.
- Written informed consent will be obtained from the participants
- Subjects will undergo HCVR testing for determining eligibility for enrolling in intervention part of the study

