10.6 MEASURES TO MINIMIZE BIAS

10.6.1 ENROLLMENT/ RANDOMIZATION/ MASKING PROCEDURES

Subjects will be screened and enrolled in two locations, neurology clinic and EMU. A total of 20 subject will be enrolled in each location and they will be randomized to drug vs placebo group equally (1:1) using computer generated random numbers. The assignment for each subject will be kept in a sealed envelope and will be provided to investigational drug pharmacy at the University of Iowa.

The participants as well as the investigators (except one) will be blinded to the drug the participant is receiving. Bottles of the study drug will be labelled with the name of study, drug A or drug B, and instruction of titration plan.

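### HCVR change from own baseline, and the per-arm change summaries, include regression to the mean and an EMU setting change; the adjusted fluoxetine-placebo difference should be the only measure of effect

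*Combined protocol and SAP*

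**What the plan says.** **Eligibility.** Section 4.1 admits patients "who have a reduced baseline HCVR slope (<2.0 L/min/mmHg"). Section 5.2 excludes "Patients with normal hypercapnic ventilatory response", defined as a slope of 2.0 or more. Section 7.3.1 states: "Subjects will undergo HCVR testing for determining eligibility for enrolling in intervention part of the study".

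**Baseline.** Section 7.1.1 states: "HCVR testing will be performed (as applicable) for baseline assessment prior to randomization and a follow up HCVR testing after randomized to an intervention arm". Section 7.3.2 lists HCVR again among the enrolment procedures but describes no separate second baseline. The schedule in 7.3.7, as far as the table can be read, marks HCVR at screening only. It also lacks the week-4 test that 7.3.3 requires, so it cannot settle the matter.

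**Setting.** Under 7.2.1, EMU participants have "baseline HCVR testing at the bedside either in a sitting up in their bed or in a chair", and clinic participants are tested in the CRU. For the retest, 4.1 says: "Subjects will return after 4 weeks for follow up HCVR testing in the Clinical Research Unit at UIHC". Section 10.6.1 says: "A total of 20 subject will be enrolled in each location and they will be randomized to drug vs placebo group equally (1:1"), so EMU participants make up half the sample.

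**Comparison.** In 4.1, "For each subject, the magnitude of post-treatment HCVR in terms of HCVR slope, minute ventilation" and the other HCVR measures are set against the subject's own baseline. Section 10.1 promises descriptive statistics by arm, to serve as estimates for later studies. The protocol summary, 10.4.3 and 10.4.11 compare fluoxetine with placebo. For slope, 10.4.3 names a linear mixed model with an interaction between HCVR slope and treatment group. For minute ventilation it uses the change from baseline. No section clearly names baseline value or enrolling location as a covariate.

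**The concern.** Patients selected because one noisy test fell below a cut-off will, on average, score higher on a second test even if nothing has changed. When the selecting test is also the baseline, that rise is counted as change. EMU participants also move from an inpatient bedside to the research unit between tests, and clinic participants do not. Any effect of setting on HCVR therefore enters the change in one half of the sample only.

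Two uses of the data are exposed. A reader of 4.1 could take a rise from own baseline as a response to fluoxetine, although some rise is expected on placebo as well. And the per-arm means and SDs of change, which 10.1 and 10.4.1 intend for planning later studies, would carry these shifts forward.

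**Working it through.** The plan has no power, effect-size or SD figure to reproduce: 10.2 states no hypothesis and 10.5 no sample size calculation.

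**Inputs from the documents.** Cut-off 2.0 L/min/mmHg (4.1, 5.2); about 100 tested (5.3); 40 randomised (protocol summary); 20 per location, 1:1 (10.6.1).

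**Assumptions, because the documents give no values.** Slope normally distributed among those tested, with the same mean and SD at retest; SD 0.5 to 1.5 (central 0.75); test-retest reliability *r* 0.5 to 0.9 (central 0.7). The share qualifying is 40% (40/100) if every qualifier is randomised, and 60% is shown because some may decline or not complete. Location shift 0.2 or 0.5; within-location SD of change 0.5 to 0.7.

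**1. Regression to the mean with no drug effect.** Expected rise = (1 - *r*) x SD x φ(z)/p, where p is the share qualifying and z its normal quantile.
- p = 0.40: φ(z)/p = 0.966. Central case: 0.3 x 0.75 x 0.966 = 0.22.
- p = 0.60: φ(z)/p = 0.644. Central case: 0.3 x 0.75 x 0.644 = 0.14.
- Range at 40%: 0.1 x 0.5 x 0.966 = 0.05 to 0.5 x 1.5 x 0.966 = 0.72.
- Range at 60%: 0.1 x 0.5 x 0.644 = 0.03 to 0.5 x 1.5 x 0.644 = 0.48.

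This applies to slope. Minute ventilation is not itself the selection variable, so it is affected only as far as it correlates with slope.

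**2. Adding a setting shift, and the effect on the drug-placebo contrast.** A simulation used 10 participants per arm per location, the central case at 40% qualifying, and a shift of +0.2 in EMU participants only.
- With no drug effect, mean change was +0.32 in both arms. In the placebo arm it was +0.42 for EMU and +0.22 for clinic participants.
- The drug-placebo difference in change averaged -0.001 when the true effect was 0, and 0.297 when it was 0.3.
- Its standard error was about 0.17, whether estimated from raw change or with baseline adjustment.

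**3. Effect of pooling on the SD of change.** With two equal locations whose mean change differs by *d*, pooled SD = √(s² + d²/4).

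| d | s | pooled SD | SD ratio | variance ratio |
|---|---|---|---|---|
| 0.2 | 0.5 | √0.260 = 0.510 | 1.02 | 1.04 |
| 0.2 | 0.7 | √0.500 = 0.707 | 1.01 | 1.02 |
| 0.5 | 0.5 | √0.3125 = 0.559 | 1.12 | 1.25 |
| 0.5 | 0.7 | √0.5525 = 0.743 | 1.06 | 1.13 |

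A later sample size scales with the variance, so it would be 2-4% too large at d = 0.2 and 13-25% too large at d = 0.5. Section 10.4.3 does not say that locations are pooled; this is inferred from the absence of any location term.

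**The case against.** The strongest reply is that the design already deals with this. The trial is randomised, double-blind and placebo-controlled, and the analysis sections compare fluoxetine with placebo. Both artefacts act on both arms and cancel in expectation, as step 2 shows. That stands. A reader might infer that the planned estimate of drug effect is biased, and the documents do not support that reading.

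Other parts of the reply also stand:
- For slope, 10.4.3 specifies a mixed model, not raw change. Its interaction term is unclear, and it cannot be counted as baseline adjustment.
- Section 7.3.2 leaves some room for a second baseline test, although basing eligibility on the baseline slope (4.1) favours a single test.
- Section 7.2.1 standardises the operator, device, headphones, blank screen, gas mixture and stopping limits. Nothing in the documents shows that setting or posture moves the slope.
- The 13-25% sample-size figure needs a location shift of 0.5, a quarter of the cut-off. With about 40 participants, the 95% interval for an SD runs from about -18% to +29%, so even a 6-12% inflation lies within sampling error.

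The reply does not remove the own-baseline comparison in 4.1, which sits beside 10.4.3 without a placebo contrast. Nor does it correct the per-arm change figures, which are a stated output.

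**Conclusion.** The point holds for within-arm change and for nothing beyond it. Change from own baseline and the per-arm summaries include regression to the mean and, for EMU participants, any setting effect. In the central case, regression to the mean alone is about 0.14 to 0.22 L/min/mmHg against a cut-off of 2.0. The wider assumptions give 0.03 to 0.72. Inflation of the planning SD is 1-2% or 6-12%, depending on the assumed location shift. The size and direction of any real setting effect are unknown.

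The fluoxetine-placebo contrast is not biased by either artefact. That protection comes from randomisation, and the per-protocol set (10.3) and the dropping of missing observations (10.4.3) could weaken it; that is a separate matter.

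This is a minor point. HCVR is a secondary endpoint in a feasibility pilot, and 10.4.1 rules out inferential tests. What is at stake is interpretation and the estimates passed to a later study.

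**What to change.** 1. In 4.1, reconcile the own-baseline comparison with 10.4.3, so that the fluoxetine-placebo difference is the only measure of drug effect.
2. In 10.4.3, estimate week-4 HCVR slope and week-4 minute ventilation by arm, with baseline value and enrolling location as covariates. This replaces the unclear interaction term for slope and the raw change for minute ventilation. The location term also covers chance imbalance if the allocation list is not balanced within location, which 10.6.1 leaves open.
3. Report the residual SD from that model as the planning SD for later studies. State that within-arm change includes retest and setting shift, with the placebo-arm change showing its size.

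The cost is wording in two sections and two model degrees of freedom: with 40 completers, 40 - 4 = 36 residual degrees of freedom instead of 40 - 2 = 38. Both covariates are already recorded. The gain in precision is likely to be modest.

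Two other remedies look attractive but do less. A common posture rule would leave the move from bedside to CRU in place. SDs by arm within location would rest on about 10 participants each, where the 95% interval for an SD is about -31% to +83%. No repeat screening test is needed.

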7.2.2 OTHER ASSAYS OR PROCEDURES

None

7.2.3 SPECIMEN PREPARATION, HANDLING, AND STORAGE

None

7.2.4 SPECIMEN SHIPMENT

NONE

7.3 STUDY SCHEDULE

7.3.1 SCREENING

Potential subjects for the study will be are referred by treating neurologists at neurology clinic & EMU at the University of Iowa Hospitals & Clinics.

- Referred subjects are screened based on review of medical history & Iowa SSRI screening questionnaire.
- Written informed consent will be obtained from the participants
- Subjects will undergo HCVR testing for determining eligibility for enrolling in intervention part of the study

7.3.2 ENROLLMENT/BASELINE

- Obtain informed consent of potential participant verified by signature on study informed consent form
- Verify inclusion/exclusion criteria.
- Obtain urine pregnancy test when applicable.
- Obtain demographic information, medical history, medication history, alcohol and tobacco use history.

Version 01.2 Protocol:201607761 Version 201.2

- Perform HCVR testing
- PHQ-9 score
- Randomize to one of the intervention arm
- Discharge randomized subjects with assigned treatment with one week of 10 mg, one week of 20 mg and 4 weeks of 40 mg pills.

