Secondary Obective:

To evaluate effect of fluoxetine on HCVR and peri-ictal respiratory

depression in drug resistant epilepsy patients.

Version 01.2 Protocol:201607761 Version 01.2

Endpoint Primary End point:

Study recruitment rate assessed every 3 months through the study

completion

Study retention rate assessed every 3 months through the study completion

Secondary End point:

Change in mood score using PHQ-9 score

Change in minute ventilation during HCVR testing

Change in slope of HCVR

Difference in duration of abnormal breathing in periocal period

Difference in oxygen saturation during periotal period

Difference in CO₂ level in periotal period

Exploratory End points: Change in VRTCO₂

Change in time to VRTCO₂

Change in time to end of HCVR testing

Population: Subjects age 18-75 years, both genders, drug resistant epilepsy with no

prior severe depression or other psychiatry co-morbidities but otherwise healthy, mostly living in State of Iowa will be screened for this study.

Phase: 2 Number of Sites 1

enrolling participants:

[figure not shown]
Description of Study Fluoxetine, given by mouth with a standard titration over 6 weeks.

Agent: 10 mg for 1 week, 20 mg for 1 week, 40 mg for 2 weeks, 20 mg for 1 week,

10 mg for 1 week then STOP

Study Duration: 2 years **Participant Duration:** 6 weeks

Version 01.2 Protocol:201607761 06/28/2017

Version 01.2 Protocol:201607761 06/28/2017

I KEY ROLES

[name]

Role: Principal investigator

Institution: The University of Iowa,

Address: [name]

[contact] Email: [contact]

[name] Role: Co-Investigator

Institution: The University of Iowa,

Address: [name]

[contact] Email: [contact]

[name] Role: Co-Investigator

Institution: The University of Iowa,

Address: [name]

[contact] Email: [contact]

[name] PhD

Role: Co-Investigator

Institution: The University of Iowa,

Address: [name]

[contact]

Email: [contact]

[name] [name] Role: Biostatistician

Institution: The University of Iowa,

Address: [name]

[contact] Email: [contact]

[name] PhD

Role: Independent Medical Examiner Institution: The University of Iowa,

Address: [name]

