• 2) To test effect of fluoxetine on peri-ictal respiratory depression: Subjects will be screened in neurlogy clinic from a group of previously diagnosed patients with epilepsy who are planned for VEEG study. Eligible subjects will undergo HCVR testing. Eligible subjects with a reduced baseline HCVR slope (<2.0 L/min/mmHg) will be enrolled and randomized to fluoxetine vs placebo (1:1) until a total of 20 subjects complete the study. Both the subjects and investigators will be blinded to the randomization process. A standard titration plan for fluoxetine & placebo will be as above, for 4 weeks prior to EMU admission. During EMU admission, the subjects will be monitored with VEEG, EKG, EMG, SpO₂, tcCO₂/ETCO₂, oral & nasal thermistor & pressure transducer to measure airway pressure, and RIP with abdominal & chest belts to measure change in circumference during respiration. Peri-ictal respiratory changes in the two groups will be compared to assess the effect of fluoxetine.

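### The capsules issued at enrolment (7.3.2) do not match the dosing schedule (6.1.7): the step-down doses are missing and 40 mg is oversupplied

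*Combined protocol and SAP*

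**What the plan says.** The dosing schedule appears in three places in the combined protocol and SAP.

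- **Protocol Summary, description of study agent:** "10 mg for 1 week, 20 mg for 1 week, 40 mg for 2 weeks, 20 mg for 1 week", followed by a final week at 10 mg and then stop.
- **6.1.7:** the same schedule. After the first weeks at 10 mg and 20 mg it continues "40 mg once a day for two weeks, 20 mg once a day for one week and 10 mg once a day for one week". Treatment ends there. Sections 6.1.5 and 6.1.9 give one dose a day for six weeks.
- **4.1:** covers only the period up to the follow-up test, and also has two weeks at the top dose: "and then 40 mg per day for 2 weeks, upon discharge". The second part of 4.1 carries this over to clinic-enrolled subjects: "A standard titration plan for fluoxetine & placebo will be as above, for 4 weeks prior to EMU admission".

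Section 6.1.8 adds one allowance, tied to a late follow-up appointment: "Subjects will be allowed to take 40 mg/day of drug vs placebo for maximum of an extra 1 week in case of delay".

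The supply handed out at enrolment is stated only in 7.3.2: "Discharge randomized subjects with assigned treatment with one week of 10 mg, one week of 20 mg and 4 weeks of 40 mg pills".

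On later dispensing the document is silent. Section 6.2 says that the investigational pharmacy "will be responsible for storing, labelling and dispensing of the drugs", with no time points. The follow-up visit in 7.3.3 includes a pill count but no issue or return of capsules, and the final contact in 7.3.4 is a telephone call at week 7.

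**The concern.** Section 7.3.2 is the instruction that staff carry out when a randomised subject goes home, and it cannot be reconciled with the schedule that the subject is told to follow. Weeks 1 to 4 are covered. For weeks 5 and 6 the subject holds only 40 mg capsules, so the planned 20 mg and 10 mg weeks cannot be taken.

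The stake is patient safety after week 4. Section 2.3.1 warns that abrupt discontinuation of fluoxetine can produce serious symptoms, and section 7.4 says that the titration was designed partly to limit withdrawal effects. The step-down is therefore a safety measure, and the supply as written removes it.

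A smaller point concerns the safety data. Adverse events collected at the week-7 call would describe a stop from 40 mg, not the planned step-down, and they enter the between-group comparison in 10.4.4.

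**Working it through.** **Inputs.** Schedule: Protocol Summary and 6.1.7. One dose a day: 6.1.5. Optional extra week at 40 mg: 6.1.8. Supply: 7.3.2. Doses = weeks × 7, summed by strength.

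**Supply and need**

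| | 10 mg | 20 mg | 40 mg | Doses | Total mg |
|---|---|---|---|---|---|
| Supply, 7.3.2 (1, 1 and 4 weeks) | 7 | 7 | 28 | 42 | 70 + 140 + 1120 = 1330 |
| Schedule, 6.1.7 (2, 2 and 2 weeks) | 14 | 14 | 14 | 42 | 140 + 280 + 560 = 980 |
| Schedule plus extra week, 6.1.8 | 14 | 14 | 21 | 49 | 140 + 280 + 840 = 1260 |
| Weeks 1 to 4 only | 7 | 7 | 14 | 28 | 70 + 140 + 560 = 770 |

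**Supply minus need**

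- Full schedule: −7 / −7 / +14
- Full schedule plus extra week: −7 / −7 / +7
- Weeks 1 to 4 only, with the step-down issued later: 0 / 0 / +14

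The 42 doses agree with six weeks of therapy, but the split by strength does not. None of the three readings gives 7/7/28. The extra week absorbs only half of the surplus. A later issue of step-down doses would explain the missing 10 and 20 mg capsules, but not the additional 14 of 40 mg.

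**What is left from the 7.3.2 supply, with full adherence**

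| Time | Used 10/20/40 | Left 10/20/40 | Still scheduled 10/20/40 | Surplus 40 mg |
|---|---|---|---|---|
| Day 21 (earliest follow-up visit) | 7/7/7 | 0/0/21 | 7/7/7 | 21 − 7 = 14 |
| Day 28 | 7/7/14 | 0/0/14 | 7/7/0 | 14 |
| Day 35, after the extra week | 7/7/21 | 0/0/7 | 7/7/0 | 7 |

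**Two ways the course could end if nothing more is issued**

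1. The subject keeps to 6.1.7 and 6.1.8 and stops from 40 mg at day 28, or at day 35 with the extra week.
2. The subject takes every capsule. That gives 28 days at 40 mg, against 14 scheduled and 21 at most with the extension, and a stop from 40 mg at day 42. The total of 1330 mg exceeds even the 1260 mg of the extended schedule.

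In both cases the last step is 40 to 0 mg instead of 10 to 0 mg.

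**Would the pill count reveal it?** Assume one capsule per daily dose. At day 28 a fully adherent subject has 42 − 28 = 14 capsules left under either supply: 7/7/0 from a 14/14/14 issue, 0/0/14 from a 7/7/28 issue. Section 6.1.2 describes the product as "Blue opaque capsule, no lettering or embossing", so a count of the total would look correct. Only a count by bottle or strength shows the mismatch.

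**The case against.** The strongest reply is that this is a slip in a visit checklist. The full schedule is stated clearly in two places, 4.1 agrees on two weeks at 40 mg, and four weeks at 40 mg appears nowhere else. Harm would require the pharmacy to fill the checklist line and not the schedule, no step-down capsules to be issued later, and nobody to notice, although 10.6.1 puts titration instructions on the bottles. Silence about a second issue proves little in a protocol that gives no dispensing dates at all. Moreover, every retained subject is seen in person near week 4: EMU-enrolled subjects return to the research unit (4.1), and clinic-enrolled subjects, about half, come in for EMU monitoring. Either occasion would allow a correction.

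Much of this stands. The line is probably a slip, the harm is conditional, and the week-4 contact is a real opportunity to put it right for all subjects. But label instructions cannot be followed with strengths that were not supplied, no dispensing is described at the follow-up visit, and the total pill count can look normal. After that visit the only scheduled contact is the telephone call at week 7. A probable slip in a dispensing instruction still needs correction, because that is the line staff act on.

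**Conclusion.** The contradiction is real and 7.3.2 is wrong as written. Against 6.1.7 the supply omits all 14 step-down doses (7 of 20 mg and 7 of 10 mg) and has 14 doses of 40 mg too many, or 7 if the extra week is used. The counts rest only on once-daily dosing and seven-day weeks. The pill-count point also assumes one capsule per daily dose.

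The safety consequence is conditional on 7.3.2 being followed and no step-down doses being issued later. It concerns subjects on fluoxetine, about 20 of the 40 planned at 1:1 allocation. The documents do not quantify the withdrawal risk, so no event rate can be attached. The week-4 HCVR and PHQ-9 measurements and the primary feasibility endpoints are essentially unaffected. It should be fixed because it bears on safety and the correction is small.

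**What to change.** Amend 7.3.2 to dispense two weeks each of 10, 20 and 40 mg (14/14/14 daily doses), plus at most one separately labelled reserve week of 40 mg for use under 6.1.8. Check the pharmacy order and the titration instructions on the bottles against 6.1.7, and do the pill count by bottle.

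If the intention is to issue the step-down doses at the follow-up visit, say so in 7.3.3, and collect only the 40 mg doses beyond those still scheduled. The visit may fall at week 3, when 7 doses of 40 mg must stay with the subject.

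The cost is one line in 7.3.2, possibly one more in 7.3.3, a pharmacy check, and the IRB approval that 12.2 requires for any amendment. Design, sample size and analysis do not change.
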